7.1.1. Alopecia Scalp Appearance Assessment (ASAA)

Protocol: ATI-502-AA-203

Subjects with patchy AA (30 - 95%) scalp hair loss at Baseline in study ATI-501-AUAT-201), will assess appearance of hair loss in the target scalp patch and the whole scalp by completing Item 1 and 2 of the ASAA-AAP: SR at the visits detailed in Schedule of Assessments (Table 3). The scalp assessment for subjects (ASAA-AAP: SR) is in Appendix 2.

Subjects with AU and AT (>95% scalp hair loss at Baseline in study ATI-501-AUAT-201) will assess the appearance of the whole scalp using the ASAA-AT/AU: SR by the subject at the visits listed in the Schedule of Assessments (Table 3). The scalp appearance for the subjects (ASAA-AT/AU: SR) is in Appendix 8.

7.1.2. Alopecia Facial Hair Appearance Assessment (AFHA) for AA, AT and AU: Subject Rating (SR) (AFHA: SR)

All subjects (AA, AT or AU) will complete the AFHA: SR. An investigational staff member will instruct the subject to assess the facial hair areas (eyebrows, eyelashes and if male, beard), educate the subject on the AFHA: SR before each evaluation at the visits detailed in Schedule of Assessments (Table 3). The staff member should not influence the subject's assessment. The AFHA: SR is in Appendix 3.

7.1.3. Subject Global Impression of Severity (SGIS)

The severity of the subject's AA, AU or AT will be assessed by all subjects at the visits detailed in Schedule of Assessments (Table 3) using the Global Impression of Severity Questionnaire in Appendix 4 for subjects with AA or Appendix 9 for subjects with AT/AU.

7.1.4. Alopecia Impact Assessment (AIA): Subject Rating

The Investigator or study staff will instruct subjects with AA, AT or AU to answer the AIA (Appendix 5) during the study visit at the visits detailed in the Schedule of Assessments (Table 3).

7.1.5. Subject Global Impression of Change (SGIC)

The investigator or study staff will instruct subjects with AA, AU or AT to answer the SGIC questionnaire at their final study treatment visit to report their overall impression of change for their condition. Subjects will assess change in the severity of their condition on a 7-point scale from "Very much improved" to "Very much worse"; the SGIC can be found in Appendix 12. Subjects should be given the baseline photo prints from study ATI-501-AUAT-201 to review to complete this assessment.

7.1.6. Subject Global Impression of Treatment Satisfaction (SGITS)

The investigator or study staff will instruct subjects with AA, AU or AT to answer the SGITS questionnaire in relation to their satisfaction with the scalp hair regrowth. Subjects will assess their satisfaction with the outcome of the study treatment on a 7-point satisfaction scale from "extremely satisfied" to "extremely dissatisfied" at the visits detailed in the Schedule of Assessments (Table 3). Subjects with patchy AA (30%-95% scalp hair loss at Baseline in study ATI-501-AUAT-201) will complete the SGITS-AAP found in Appendix 6. Subjects with AT or

Date: 09NOV2018, Version 1.0 Page 37 of 80 CONFIDENTAL

AU (> 95% scalp hair loss at Baseline in study ATI-501-AUAT-201) will complete the SGITS-AT/AU found in Appendix 10.

7.1.7. Subject Global Satisfaction with Hair Quality (SGSHQ)

The investigator or study staff will instruct the subject to answer the SGSHQ questionnaire in relation to their satisfaction with the quality of scalp hair right now. Subjects will assess their satisfaction with the quality of their scalp hair on a 7-point satisfaction scale from extremely satisfied to extremely dissatisfied at the visits detailed in the Schedule of Assessments (Table 3). Subjects with patchy AA (30%-95% scalp hair loss at Baseline in study ATI-501-AUAT-201) will complete the SGSHQ-AAP found in Appendix 7. Subjects with AT or AU (> 95% scalp hair loss at Baseline in study ATI-501-AUAT-201) will complete the SGSHQ-AT/AU found in Appendix 11.

7.2. Investigator Efficacy Assessments

The investigator will complete the assessments detailed in Table 6 in the order listed.

Table 6: Investigator Assessments

Protocol: ATI-502-AA-203

Order	Subjects with Patchy AA (30% – 95% scalp hair loss at Baseline in study ATI-501-AUAT-201)	Subjects with AU or AT (>95% scalp hair loss at Baseline in study ATI-501- AUAT-201)							
1.	Alopecia Scalp Appearance Assessment for Patchy AA: Clinician Rating (ASAA-AAP: CR)	Alopecia Scalp Appearance Assessment for AT/AU: Clinician Rating (ASAA-AT/AU: CR)							
2.	Alopecia Facial Hair Appearance Assessm	ent: Clinician Rating (AFHA: CR)							
3.	Non-Scalp Hair Loss Assessment (NSHA)								
4.	Physician Global Impression of Severity for Patchy AA (PhGIS-AAP)	Physician Global Impression of Severity for AT/AU (PhGIS-AT/AU)							
5.	Physician Global Impre	ession of Change (PhGIC)*							
6.	Hair Quality Assessment	N/A							
7.	SALT								
8.	ALODEX								
9.	Vellus and Indeterminate Hair Assessment								

^{*}Only assessed at final study treatment visit

7.2.1. Alopecia Scalp Appearance Assessment (ASAA) Clinician Rating (CR)

The investigator will complete the ASAA-AAP: CR for subjects with patchy AA (30%-95% scalp hair loss at Baseline in study ATI-501-AUAT-201) or the ASAA-AT/AU: CR for subjects

Date: 09NOV2018, Version 1.0 Page 38 of 80 CONFIDENTAL

with AT or AU (>95% scalp hair loss at Baseline in study ATI-501-AUAT-201) at the visits listed in Table 3, Schedule of Assessments.

For subjects with patchy AA (30% to 95% scalp hair loss at Baseline in study ATI-501-AUAT-201), the appearance of the target scalp patch and the whole scalp will be assessed by the Investigator by completing Items 1 and 2 of the ASAA-AAP:CR (Section 7.2.1.1).

For subjects with AT or AU (scalp hair loss > 95% at Baseline in study ATI-501-AUAT-201), the appearance of the whole scalp will be assessed by the investigator by completing the ASAA-AT/AU: CR (Section 7.2.1.2).

7.2.1.1. Alopecia Scalp Appearance Assessment (ASAA) for Patchy AA: Clinician Rating (CR) (ASAA-AAP: CR)

Rating (CR) (HOIM-IMI : CR)
Instructions for item 1: Please mark an "X" in the box () that best describes the appearance of the subject's target patch right now. Please select the one response that best represents your answer.
Full hair, scalp of the target patch completely covered with hair
Most hair, scalp of the target patch mostly covered with hair
Some hair, scalp of the target patch somewhat covered with hair
A little hair, scalp of the target patch mostly exposed
☐ No hair, scalp of the target patch completely exposed
Instructions for item 2: Please mark an "X" in the box () that best describes the appearance of the subject's whole scalp right now. Please select the one response that best represents your answer.
☐ Full hair, whole scalp completely covered with hair
☐ Most hair, whole scalp mostly covered with hair
Some hair, whole scalp somewhat covered with hair
A little hair, whole scalp mostly exposed
☐ No hair, whole scalp completely exposed
7.2.1.2. Alopecia Scalp Appearance Assessment (ASAA) for AT and AU: Clinician Rating (CR) (ASAA-AT/AU: CR)
Instructions: Please mark an "X" in the box () that best describes the appearance of the subject's whole scalp right now. Please select the one response that best represents your answer.
☐ Full hair, whole scalp completely covered with hair
Most hair, whole scalp mostly covered with hair
Some hair, whole scalp somewhat covered with hair

Date: 09NOV2018, Version 1.0 Page 39 of 80 CONFIDENTAL

A little hair, whole scalp mostly exposed
☐ No hair, whole scalp completely exposed
7.2.2. Alopecia Facial Hair Appearance Assessment (AFHA) for AA, AT and AU: Clinician Rating (CR) (AFHA: CR)
For subjects with AA, AU or AT, the appearance of the subject's facial hair (eyebrows, eyelashes and if male, beard) will be assessed using the AFHA: CR by the investigator at the visits listed in the Schedule of Assessments (Table 3).
The AFHA: CR is the investigator's assessment of the subject's facial hair (eyebrow(s), eyelashed and if male, beard) at a particular point in time. The investigator should NOT refer to any other assessments to assist with these assessments. The investigator or designee will assess the affected facial hair areas (eyebrows, eyelashes and if male, beard) using the scales below and report the one esponse that best describes the amount of eyebrow, eyelash and if applicable beard hair present. Right and left eyebrow and eyelashes should be evaluated separately. The AFHA is a tool to assess the presence of hair in expected areas of growth. As such, unexpected hair growth (e.g. facial/bear hair in women) should be documented as an adverse event rather than on the AFHA.
Instructions for item 1a: Please mark an "X" in the box () that best describes the appearance of the subject's left eyebrow hair right now. Please select the one response that best represents your answer.
Full eyebrow hair
☐ Most eyebrow hair
Some eyebrow hair
A little eyebrow hair
☐ No eyebrow hair
Instructions for item 1b: Please mark an "X" in the box () that best describes the appearance of the subject's right eyebrow hair right now. Please select the one response that best represents your answer.
☐ Full eyebrow hair
☐ Most eyebrow hair
Some eyebrow hair
A little eyebrow hair
☐ No eyebrow hair

Aclaris Therapeutics, Inc.

Date: 09NOV2018, Version 1.0 Page 40 of 80 CONFIDENTAL

Protocol: ATI-502-AA-203

Instructions for item 2a: Please mark an "X" in the box () that best describes the appearance of the subject's **left** eyelashes right now. Please select the one response that best represents your answer. Full eyelashes Most eyelashes Some eyelashes A little eyelashes No eyelashes **Instructions for item 2b:** Please mark an "X" in the box () that best describes the appearance of the subject's **right** eyelashes right now. Please select the one response that best represents your answer. Full eyelashes Most eyelashes Some eyelashes A little eyelashes ☐ No eyelashes **Instructions for item 3:** Please mark an "X" in the box () that best describes the appearance of the subject's beard hair right now. Beard hair can include hair on the chin, cheeks, neck, and above the upper lip. Please select the one response that best represents your answer. Full beard hair Most beard hair Some beard hair A little beard hair No beard hair

Aclaris Therapeutics, Inc.

Date: 09NOV2018, Version 1.0 Page 41 of 80 CONFIDENTAL

Protocol: ATI-502-AA-203

Aclaris Therapeutics, Inc.

7.2.3. Non-Scalp Hair Loss Assessment (NSHA)

Protocol: ATI-502-AA-203

The investigator will assess body hair (axillary, truncal, genital, extremities) and facial hair including nasal hair using a 3-point scale; no hair loss, some hair loss and total hair loss. Nasal hair will be assessed by presence or absence only. These assessments will be completed at the visits listed in the Schedule of Assessments (Table 3) (Olsen, 2011).

Instructions: Please mark an "X" in the box () that best describes the appearance of the subject's body hair loss right now. Please select the one response that best represents your answer.

Mark "X"	Body Hair Loss (axillary, truncal, genital, extremities)						
	В0	No body hair loss					
	B1	Some hair loss					
	B2	Total body hair loss					

Instructions: Please mark an "X" in the box () that best describes the appearance of the subject's nasal hair loss right now. Please select the one response that best represents your answer.

Mark "X"	Nasal Hair Loss	
	NH0	No nasal hair loss
	NH1	Some to total nasal hair loss

7.2.4. PHYSICIAN GLOBAL IMPRESSION OF SEVERITY (PhGIS)

The severity of the subject's AA, AU or AT will be assessed at the visits detailed in Schedule of Assessments (Table 3), by the investigator using either the PhGIS-AAP for subjects with patchy AA (30% - 95% scalp hair loss at Baseline in study ATI-501-AUAT-201) (Section 7.2.4.1) or the PhGIS-AT/AU for subjects with AT or AU (> 95% scalp hair loss at Baseline in study ATI-501-AUAT-201) (Section 7.2.4.2).

Date: 09NOV2018, Version 1.0

Protocol: ATI-502-AA-203 Aclaris Therapeutics, Inc. 7.2.4.1. PHYSICIAN GLOBAL IMPRESSION OF SEVERITY (PhGIS-AAP) Please mark an "X" in the box () that best describes the severity of the subject's patchy alopecia areata right now. Overall, how severe is the subject's patchy alopecia areata right now? Mild Moderate Severe ☐ Very Severe Extremely Severe 7.2.4.2. PHYSICIAN GLOBAL IMPRESSION OF SEVERITY (PhGIS-AT/AU) Please mark an "X" in the box () that best describes the severity of the subject's alopecia totalis or alopecia universalis right now. Overall, how severe is the subject's alopecia totalis or alopecia universalis right now? Mild Moderate Severe Very Severe Extremely Severe 7.2.5. Physician Global Impression of Change (PhGIC) The investigator will assess the global impression of change in the subject's hair loss (AA, AT or AU) at Week 24 (Visit 6) using the PhGIC detailed below and referencing the baseline photos from study ATI-501-AUAT-201. Compared to the subject's hair loss at Baseline [prior to study medication initiation on study ATI-501-AUAT-201], the subject's AA, AT or AU is (Please mark an "X" in the box \(\sigma\): 1=Very much improved since the initiation of treatment; 2=Much improved; 3=Minimally improved;

Date: 09NOV2018, Version 1.0 Page 43 of 80 CONFIDENTAL

5=Minimally worse;

6= Much worse;

4=No change from baseline (the initiation of treatment);

7=Very much worse since the initiation of treatment.

7.2.6. Hair Quality Assessments

Hair quality will be assessed by the investigator using the hair pull test including the presence of exclamation point hairs at the visits detailed in Schedule of Assessments (Table 3). For subjects with AU or AT (>95% scalp hair loss at Baseline in study ATI-501-AUAT-201), the hair pull test will not be conducted.

7.2.6.1. Hair Pull Test

Protocol: ATI-502-AA-203

The hair pull test is performed at the edge of the alopecic (target) patch as follows:

- Pinch 25 to 50 hairs between non-gloved thumb and forefinger and exert slow, gentle traction while sliding fingers up.
- Resulting extracted hairs should be examined with magnification and counted.
 - Normal: 1 to 2 hairs dislodged
 - Abnormal: >2 hairs dislodged
 - Broken hairs (structural disorder)
 - Broken-off hair at the borders of an alopecic patch that are easily removable (in alopecia areata) (exclamation point hair)

7.2.7. Severity Alopecia Tool (SALT) Score

The SALT score is a measurement of the amount of terminal scalp hair loss. The investigator will assess the SALT score using an iPad provided by Aclaris at the visits detailed in Schedule of Assessments (Table 3). The SALT score must be determined prior to the ALODEX score. Equipment, supplies, training and the detailed Reference Guide will be provided to the investigational site prior to the initiation of subject enrollment.

7.2.8. Alopecia Density and Extent Score (ALODEX)

The ALODEX score is a measurement of the amount of terminal scalp hair loss. The investigator will calculate the ALODEX score using the iPad provided by Aclaris at the visits detailed in Schedule of Assessments (Table 3). The ALODEX score must be determined after the SALT score. Equipment, supplies, training and the detailed Reference Guide will be provided to the investigational site prior to the initiation of subject enrollment.

7.2.9. Vellus and Indeterminate Hair Assessment

The investigator will assess if vellus and indeterminate hair are present on the scalp by completing the question:

Is vellus hair present in the areas of hair loss? Y, N

Is indeterminate hair present in the areas of hair loss? Y, N

Hair types are characterized by the diameter and length of the hair shafts. Vellus hair is soft, hypopigmented, unmedullated and less than 0.03 mm in diameter and less than 1 cm in length. Terminal hair is longer, coarser, often medullated, pigmented, and > 0.06 mm in diameter and > 1 cm in length. Indeterminate hairs are intermediate in size between terminal and vellus hairs (>0.03 mm and <0.06 mm in diameter).

Date: 09NOV2018, Version 1.0 Page 44 of 80 CONFIDENTAL

7.3. Photographic Assessment

Protocol: ATI-502-AA-203

A qualified investigational staff member will take standardized photographs of the scalp at the visits detailed in Schedule of Assessments (Table 3). The photographs are to document loss, maintenance, or increase of hair growth during treatment. Photography is a required element of the study procedures and is not considered optional. During initial study discussion as part of consent procedures, site staff should ensure that subjects are fully aware of this aspect of study participation.

Subjects should be instructed to maintain the same hairstyle and color throughout the study. It is important for the staff member to clip the hair as detailed in the instructions provided, so the areas of hair loss and possible regrowth are visible at the post-baseline study visits. Equipment, supplies, training and detailed instructions for obtaining and managing photographs and clipping the hair will be provided to the investigational center prior to the initiation of subject enrollment.

Date: 09NOV2018, Version 1.0 Page 45 of 80 CONFIDENTAL

8. ASSESSMENT OF SAFETY

8.1. Safety Parameters

Protocol: ATI-502-AA-203

Safety will be assessed throughout the study by the investigator or a designated and appropriately trained staff member.

8.1.1. Demographic/Medical History/ Alopecia Areata History

The study site staff will review and if necessary, update the demographic, medical history and alopecia history obtained in study ATI-501-AUAT-201 and record into the source document and eCRF for study ATI-502-AA-203. Any adverse events that were ongoing at completion of Visit 9 in ATI-501-AUAT-201 will be recorded as medical history in the ATI-502-AA-203 eCRF. Adverse Events that started and resolved during the course of study ATI-501-AUAT-201 do not need to be reported as medical history unless the investigator considers the event(s) to be clinically significant in relation to the subject's continuation in study ATI-502-AA-203. The medical history of women who are not of childbearing potential should reflect the reason e.g. post-menopausal for 1 year or greater, bilateral tubal ligation, or hysterectomy. The subject's alopecia history (Appendix 1) is captured on a separate source document and eCRF and is not documented as part of the subject's general medical history.

8.1.2. Vital Signs

Vital signs will be measured at each visit during the study. The following items will be measured:

- Body temperature
- Pulse rate
- Respiration rate
- Blood pressure (systolic and diastolic) after the subject sits quietly for at least 5 minutes

Any measure that is, in the opinion of the investigator, abnormal AND clinically significant (CS) must be recorded as medical history if found prior to the first study medication administration, or as an AE if found after the first dose of study medication.

A systolic blood pressure >140mm Hg or a diastolic blood pressure >90 mmHg is considered abnormal and therefore must be defined as CS or not clinically significant (NCS) in the eCRF.

8.1.3. Physical Examination

The investigator or designee will perform a physical examination for all body systems at the end of treatment Week 24 (Visit 6). A physical examination may also be performed at Visit 1 if the Visit 1 did not occur at Visit 9 of the ATI-501-AUAT-201 study. The skin assessment portion of the Physical Examination does not require documentation of alopecia as an abnormality since it is the indication of interest for this study and required for participation. In the absence of any other abnormalities, skin should be considered "Normal" for these subjects.

Date: 09NOV2018, Version 1.0 Page 46 of 80 CONFIDENTAL

8.1.4. Electrocardiogram (ECG)

Protocol: ATI-502-AA-203

Any abnormalities arising from ECGs collected during the ATI-501-AUAT-201 study that are, in the opinion of the investigator, clinically significant, must be reported as medical history on the ATI-502-AA-203 study.

8.1.5. Clinical Laboratory Assessments

A qualified staff member will collect non-fasting samples for clinical laboratory analysis at the visits detailed in Schedule of Assessments (Table 3). Samples will be sent to a central laboratory for analysis. Refer to the study specific laboratory manual for handling and shipping instructions. The following tests will be conducted:

Chemistry Panel

Albumin

Alkaline phosphatase

Alanine aminotransferase (ALT)

Aspartate aminotransferase (AST)

Blood urea nitrogen (BUN)

Bicarbonate

Calcium

Chloride

Creatinine

Glucose

Lactate dehydrogenase (LDH)

Phosphorus

Potassium

Sodium

Total bilirubin

Total protein

Uric acid

CPK

Crk

Total cholesterol, LDL, HDL,

Triglycerides

Urine Pregnancy Test for WOCBP

(At the visits detailed in Schedule of

Assessments (Table 3)).

Complete Blood Count

Hematocrit

Hemoglobin

Platelet count

Red blood cell morphology

Red blood cell count

White blood cell count

White blood cell differential

% & absolute

Basophils

Eosinophils

Lymphocytes

Monocytes

Neutrophils

Urinalysis

Total cholesterol, LDL, HDL and Triglycerides will be assessed at all visits. The results of the clinical laboratory tests will be reported on the central laboratory's standard reports. The investigator must note NCS or CS to define the clinical relevance of any result that is outside the normal range for the laboratory. The investigator must date and initial every laboratory report.

Date: 09NOV2018, Version 1.0 Page 47 of 80 CONFIDENTAL

The investigator or subinvestigator must review all the laboratory test results against the study entry criteria and the Study Medication Interruption Criteria Table 2 for each subject. Subjects with laboratory values meeting the Study Medication Interruption Criterial found in Table 2 must have repeat laboratory testing performed with results meeting the minimum criteria for resumption.

The investigator must report all laboratory results from samples collected on the ATI-502-AA-203 study that are BOTH outside the normal range for the laboratory AND, in the opinion of the investigator, CS as an AE. Laboratory results from samples collected at V9 on the ATI-501-AUAT-201 study that are BOTH outside the normal range for the laboratory AND, in the opinion of the investigator, CS must be reported as medical history on the ATI-502-AA-203 study eCRF. The investigator must review all laboratory reports in a timely manner.

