8.2.1. Definition of Adverse Events

8.2.1.1. Adverse Event (AE)

An AE is the development of an undesirable medical condition or the deterioration of a preexisting medical condition following or during exposure to a pharmaceutical product, whether or not considered casually related to the product.

The investigator should, when certain, report a diagnosis rather than the signs, symptoms or clinically significant abnormal laboratory values associated with the AE. Otherwise, signs, symptoms or abnormal laboratory values may be used to describe the AE.

Every new episode or clinically significant worsening of a chronic condition (e.g., headaches, seasonal allergies, depression, or hypertension) should be reported as a separate AE, even if the condition is reported in the subject's medical history. Hair growth in unexpected areas, such as facial hair in women, should be reported as an adverse event.

Any CS abnormality discovered prior to the first study medication treatment (e.g. laboratory or ECG results from Visit 9 in study ATI-501-AUAT-201) should be reported as medical history, not as an AE.

All AEs that occur after any subject has been enrolled, before treatment, during treatment, or within 30 days following the cessation of treatment, whether or not they are related to the study, must be recorded in the subject's source documents and in the Aclaris' electronic case report

Date: 09NOV2018, Version 1.0 Page 48 of 80 CONFIDENTAL

Protocol: ATI-502-AA-203

form (eCRF). Changes to a subject's medical condition that occur between signing an ICF and beginning treatment should be captured in the medical history.

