9.5. Safety Analyses

Protocol: ATI-502-AA-203

Safety analyses will include descriptive statistics calculated on the safety parameters using the safety population. The proportion of subjects with treatment-emergent adverse events will be tabulated and presented by Medical Dictionary for Regulatory Activities (MedDRA) System Organ Class. Vital signs and clinically significant abnormal laboratory results will also be tabulated.

Data from all enrolled subjects will be presented and summarized. Safety summaries will include listings of adverse events incidences within each MedDRA System Organ Class, and changes from pre-dose values in vital signs. Adverse event summaries will be presented showing the proportion of subjects experiencing adverse events, both overall and by MedDRA System Organ Class.

Date: 09NOV2018, Version 1.0 Page 55 of 80 CONFIDENTAL

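### Section 8.1.5 makes every clinically significant on-study laboratory value an AE without asking whether it is new or worse, which conflicts with the AE definition in Section 8.2.1.1

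*Combined protocol and SAP*

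**What the plan says.** Section 8.1.5 sorts laboratory results by the study in which the sample was taken. For on-study samples, "The investigator must report all laboratory results from samples collected on the ATI-502-AA-203 study that are BOTH outside the normal range for the laboratory" and CS are to be reported as an AE. For Visit 9 samples from the oral study, a result that is out of range and "CS must be reported as medical history on the ATI-502-AA-203 study eCRF".

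Section 8.2.1.1 sorts by change in the subject's condition: "An AE is the development of an undesirable medical condition or the deterioration of a preexisting medical condition following or during exposure". For conditions already in the history, what is reported separately is "Every new episode or clinically significant worsening of a chronic condition". For CS abnormalities discovered before the first treatment it gives as examples "laboratory or ECG results from Visit 9 in study ATI-501-AUAT-201) should be reported as medical history, not as an AE". Sections 8.1.1 and 8.3.1 likewise send AEs still ongoing from the oral study to medical history.

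For vital signs, Section 8.1.2 says that a CS abnormality "must be recorded as medical history if found prior to the first study medication administration, or as an AE if found after the first dose".

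Section 9.5 says: "The proportion of subjects with treatment-emergent adverse events will be tabulated". It does not define treatment-emergent, and Table 1 only expands the abbreviation TEAE.

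**The concern.** Visit 1 is normally the same day as Visit 9 of the oral study (Table 3, footnote 1), so topical treatment starts with no gap after 24 weeks of ATI-501 or placebo suspension. ATI-501 is a prodrug of ATI-502 (Section 1.5). A laboratory abnormality present at Visit 9 may still be there at the first scheduled on-study sample at Week 4.

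Whether that persisting value is an AE depends on which section the site follows. Two sites with identical data could report different AE counts. Safety is named first in the primary objective (Section 2.1), and there is no concurrent control group against which carry-over could be recognised. The summaries by prior treatment are specified for efficacy evaluations (Synopsis, Statistical Methods), so no planned safety table would separate carry-over from the oral phase.

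**Working it through.** The documents give no rate of CS abnormalities at Visit 9 and no expected AE rate, so there is no stated figure to reproduce. The check is a comparison of the rules.

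**Step 1. Apply both rules to each pattern of results (Visit 9, then an on-study sample).**

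| Visit 9 | On-study sample | Section 8.1.5 | Section 8.2.1.1 |
|---|---|---|---|
| Not CS | CS | AE | AE (development) |
| CS | CS, worse | AE | AE (deterioration) |
| CS | CS, unchanged | AE | Medical history only |
| CS | CS, improving | AE | Medical history only |
| CS | Normal or not CS | No AE | No AE |

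The rules disagree only in the third and fourth rows.

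**Step 2. Can those rows occur?** Section 4.2 sets no laboratory limits of its own; its first criterion excludes subjects who met the oral study's discontinuation criteria. Section 3.4.1.1 allows treatment to begin once Table 2 values meet the resumption limits, which include AST or ALT below 2 x ULN and creatinine below 1.5 x ULN. Values above the normal range can satisfy both. Entry with an out-of-range result is therefore possible; whether it is CS is left to the investigator.

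**Step 3. Would the analysis remove them?** An AE dated to an on-study sample begins after the first dose. Under the common convention of counting AEs by onset date, it would be treatment-emergent. Section 9.5 neither adopts nor rejects that convention. It plans changes from pre-dose values for vital signs but states none for laboratory results.

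**Step 4. Illustration with assumed rates.** Let N = 80 (Section 9.1, all assumed treated), q = the share with a CS Visit 9 abnormality that persists without worsening, and p = the share with a truly new CS abnormality, assumed to be 5% and independent of carry-over. If 8.1.5 is followed literally:

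- expected carry-over subjects = 80q
- probability of at least one = 1 − (1 − q)^80
- apparent share with an AE = 1 − (1 − p)(1 − q)

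| q (assumed) | Expected subjects | P(at least one) | Apparent share |
|---|---|---|---|
| 1% | 0.8 | 0.55 | 5.95% |
| 2.5% | 2.0 | 0.87 | 7.4% |
| 5% | 4.0 | 0.98 | 9.75% |
| 10% | 8.0 | >0.99 | 14.5% |

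Under 8.2.1.1 the share stays at 5% in every row. One subject is 1/80 = 1.25 percentage points, or less if that subject already has another AE.

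**The case against.** The strongest reply is that the protocol already answers the question. Section 8.2.1.1 defines an AE, an unchanged value does not meet the definition, and Visit 9 laboratory results are named there as medical history. On that reading 8.1.5 only separates Visit 9 samples from later ones. This defeats the inference that the protocol as a whole counts carried-over abnormalities as topical AEs. It does not remove the conflict: 8.1.5 is the specific laboratory instruction, it is mandatory and covers all such results, and the medical-history sentence in 8.2.1.1 addresses the abnormality when discovered, not a later CS repeat.

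A reader might also infer that 8.1.2 sets the same rule for vital signs. It does not. Its test is when the abnormality is found, and one seen at Visit 9 was found before the first dose. It is at most silent on an unchanged repeat. Pre-existing high blood pressure is a poor example, because 8.2.1.1 lists hypertension among the chronic conditions that call for a separate AE on a new episode or clinically significant worsening.

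A reader might expect the excess mainly in subjects who took ATI-501. The documents do not show this. Section 1.3 reports no clinically significant laboratory abnormalities with oral dosing, although in healthy volunteers over a much shorter period.

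Other mitigating facts stand. Subjects must be in good general health. An investigator may rate a stable abnormality as not CS. Any carry-over AE should have a matching medical-history entry that exposes it. The error would be over-reporting, in a descriptive study with no inferential analyses.

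**Conclusion.** The point holds as an internal conflict with a possible effect on the AE count. Section 8.1.5 lacks a new-or-worsened condition, 8.2.1.1 has one, nothing ranks them, and 9.5 does not define treatment-emergent in a way that settles it. The effect is limited to laboratory values that were CS at Visit 9 and remain CS without worsening.

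Its size cannot be derived from the documents. Depending on the assumed carry-over rate, it runs from under one subject in 80 (q = 1%) to eight (q = 10%), and it is zero wherever 8.2.1.1 is followed. Those figures assume literal use of 8.1.5 and AE onset dated to the on-study sample. The primary SALT endpoint is not affected. For vital signs the conclusion goes no further than an ambiguity in 8.1.2.

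**What to change.** 1. In 8.1.5, require an AE only when the CS value is new or has worsened from the last value before first topical application (Visit 9, or the repeated Visit 1), consistent with 8.2.1.1. A persisting, non-worsened value stays in medical history and continues to be followed.
2. In 8.1.2, add the same clarifying words for unchanged repeat vital signs.
3. In 9.5, state that treatment-emergent means new or worsened after first topical application.
4. Tabulate persisting pre-existing CS values separately from emergent ones, so that no safety information is lost.

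The cost is a few sentences in the protocol and matching eCRF guidance. Visit 9 assessments are already to be entered in this study's eCRF for Visit 1 (Table 3, footnote 1), so no new data are needed. The small downside is that the investigator must judge worsening against the pre-dose value.
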